5.4.10. Criteria for Permanent Discontinuation of Study Treatment

The occurrence of unacceptable toxicity not caused by the underlying malignancy will be presumed to be related to study treatment administration and will require that the study treatment be permanently discontinued. Unacceptable toxicity is defined as follows:

- Occurrence of an AE that is related to treatment with the study treatment that, in the judgment of the investigator or the medical monitor, compromises the subject's ability to continue study-specific procedures or is considered to not be in the subject's best interest.
- An AE requiring more than 2 dose reductions of INCB001158 or epacadostat.
- Persistent AE requiring a delay of therapy for more than 4 weeks unless a greater delay has been approved by the sponsor, or persistent irAEs (described in [Table 9](#)) requiring a delay of therapy for more than 12 weeks.

5.5. Withdrawal of Subjects From Study Treatment

5.5.1. Withdrawal Criteria

Subjects **must** be withdrawn from study treatment for the following reasons:

- The subject becomes pregnant.
- Consent is withdrawn. Subjects may choose to withdraw from the study at any time without penalty of jeopardizing their health care or loss of benefits to which the subject is otherwise entitled. Note: Consent withdrawn means that the subject can no longer be followed and no additional data can be collected. Subjects may choose to discontinue study treatment and remain in the study to be followed for progression and survival.
- Further participation would be injurious to the subject's health or well-being, in the investigator's medical judgment.
- Unacceptable toxicity (see Sections 5.4.6, 5.4.9, and 5.4.10). Subjects with unacceptable toxicities must be withdrawn from study treatment but will continue in the follow-up period of the study (see Section 6.4).
- The study is terminated by the sponsor.
- The study is terminated by the local health authority, IRB, or IEC.

A subject **may** be discontinued from study treatment as follows:

- Confirmed radiographic progression of disease per RECIST v1.1 (see Section 7.7.1.2). A subject may be granted an exception to continue on treatment with confirmed radiographic progression if clinically stable or clinically improved (see Sections 7.7.1.2 and 7.7.1.5).

Note: For unconfirmed progression see Section 7.7.1.2.

- If, during the course of the study, a subject is found not to have met eligibility criteria (see Section 3), the medical monitor, in collaboration with the investigator, will determine whether the subject should be withdrawn from the study.
- If a subject is noncompliant with study procedures or study treatment administration in the investigator's opinion, the sponsor should be consulted for instruction on handling the subject.

5.5.2. Withdrawal Procedures

In the event that the decision is made to permanently discontinue the study treatment, the subject will be withdrawn, and the EOT visit should be conducted. Reasonable efforts should be made to have the subject return for a follow-up visit. These visits are described in Section 6. The last date of the last dose of study treatment and the reason for subject withdrawal will be recorded in the eCRF.

If a subject is withdrawn from the study treatment:

- The study monitor or sponsor must be notified.
- The reason(s) for withdrawal must be documented in the subject's medical record and in the eCRF.
- The EOT visit should be performed.
- The date of the EOT visit should be recorded in the eCRF and IRT.
- Subjects must be followed for safety until the time of the follow-up visit or until study treatment–related toxicities resolve, return to baseline, or are deemed irreversible, whichever is longest.
- Subjects who discontinue for reasons other than disease progression will continue to be followed for disease status as outlined in Section 6.4.2.
- [REDACTED]

If the subject discontinues study treatment and actively withdraws consent for collection of follow-up data (safety follow-up or disease assessment), then no additional data collection should occur; however, subjects will have the option of withdrawing consent for study treatment but continuing in the follow-up period of the study for safety/efficacy assessments.

5.6. Concomitant Medications

All concomitant medications and treatments must be recorded in the eCRF. Any prior medication received up to 21 days before the first dose of study treatment and 30 days after the last dose of study treatment, or until the subject begins a new anticancer therapy, whichever occurs first, will be recorded in the eCRF. Any addition, deletion, or change in the dose of these medications will also be recorded. Concomitant medications administered after 30 days after the last dose of study treatment should be recorded for SAEs as defined in Section 8. Concomitant treatments/procedures that are required to manage a subject's medical condition during the study will also be recorded in the eCRF.

5.6.1. Permitted Medications

All treatments that are not excluded in the Protocol and the investigator considers necessary for a subject's welfare may be administered at the discretion of the investigator in keeping with the community standards of medical care. All concomitant medication will be recorded on the eCRF including all prescription, over-the-counter, herbal supplements, and IV medications and fluids. If changes occur during the study period, documentation of drug dosage frequency, route, and date will also be included on the eCRF.

Palliative and supportive care is permitted during the course of the study for underlying medical conditions and management of symptoms. Surgery for tumor control is not permitted during the study. Palliative radiotherapy is permitted to a limited number of lesions if considered medically necessary by the treating physician as long as the lesions are NOT a RECIST v1.1-defined target lesion. Study therapy should be held during the course of palliative radiotherapy and should be

resumed no earlier than the next scheduled administration of study therapy. The specifics of the radiation treatment, including the location, will be recorded.

Note: The use of bisphosphonates and denosumab are permitted in this study.

5.6.2. Restricted Medications and Measures

Use of coumarin-based anticoagulants (eg, warfarin) is discouraged. Low-dose warfarin (1 mg) is acceptable; however, doses that increase the INR are discouraged and may require dose modification. If an alternative to coumarin-based anticoagulants cannot be used, investigators should follow the guidelines in [Table 13](#) and either closely monitor or closely monitor and reduce the subject's dose of coumarin-based anticoagulant upon initiating therapy with epacadostat. The INR should be monitored weekly for the first 4 weeks after initiation of therapy and upon discontinuation of epacadostat.

Table 13: Warfarin Dose Adjustment Recommendation When Initiating Concurrent Epacadostat Treatment

Stable INR	Epacadostat Dose
	≤ 100 mg BID
INR ≤ 2.5	Close INR monitoring
INR > 2.5	Close INR monitoring

5.6.3. Prohibited Medications

Medications or vaccinations specifically prohibited in the exclusion criteria are not allowed during the ongoing study. If there is a clinical indication for any medication or vaccination specifically prohibited during the study, discontinuation from study therapy may be required. The investigator should discuss any questions regarding this with the medical monitor. The final decision on any supportive therapy or vaccination rests with the investigator and/or the subject's primary physician. However, the decision to continue the subject on study treatment requires the mutual agreement of the investigator, the medical monitor, and the subject.

Subjects are prohibited from receiving the following therapies during the screening and treatment periods of this study:

- Antineoplastic systemic chemotherapy or biological therapy not specified in this Protocol.
- Immunotherapy not specified in this Protocol.
- Investigational agents other than INCB001158, epacadostat, and pembrolizumab.
- Oncologic surgery for tumor control.
- Radiation therapy for disease control.
 - *Note:* Radiation therapy to symptomatic lesions or to the brain may be allowed at the investigator's discretion, provided the lesions were not previously defined by the site as target lesions.

- Live vaccines within 30 days before the first dose of study treatment and while participating in the study.
 - Examples of live vaccines include, but are not limited to, the following: measles, mumps, rubella, chickenpox, yellow fever, nasal seasonal flu, nasal H1N1 flu, rabies, BCG, and typhoid.
- Except for erythropoietin or darbepoetin alpha (Aranesp[®]), use of growth factors (ie, G-CSF, GM-CSF, etc.) is not permitted in the first treatment cycle unless the subject experiences a hematologic DLT.
- Concomitant treatment with valproic acid/valproate-containing therapies is not permitted as hyperammonemia is a well-described toxicity of valproic acid, particularly at high exposures, potentially through inhibition of the urea cycle (Verrotti et al 2002, Wadzinski et al 2007).
- Concomitant treatment with allopurinol or other xanthine oxidase inhibitors is not allowed. Xanthine oxidase inhibitors (eg, allopurinol) cause an accumulation of orotic acid in the urine, which would confound the assessment of safety in these subjects.
- Any MAOI or drug associated with significant MAO inhibitory activity agents is prohibited from 21 days before starting study treatment through 2 weeks after the final dose of epacadostat has been taken. See [Appendix C](#) for prohibited medications associated with MAO inhibition.
- Any UGT1A9 inhibitor, including, but not limited to acitretin, amitriptyline, androsterone, cyclosporine, dasatinib, diclofenac, diflunisal, efavirenz, erlotinib, flutamide, gefitinib, gemfibrozil, glycyrrhetic acid, glycyrrhizin, imatinib, imipramine, ketoconazole (systemic), linoleic acid supplements, mefenamic acid, mycophenolic acid, niflumic acid, nilotinib, phenobarbital, phenylbutazone, phenytoin, probenecid, quinidine, ritonavir, sorafenib, sulfinpyrazone, valproic acid, and verapamil.
- Prolonged therapy with systemic glucocorticoids (> 7 days) for any purpose other than to modulate symptoms from an AE, SAE, or event of clinical interest, or for use as a premedication for chemotherapy or in participants with a known history of an IV contrast allergy administered as part of CT radiography. Brief, limited use of systemic corticosteroids (≤ 7 days) are permitted where such use is considered standard of care (eg, for COPD exacerbation).
 - Replacement doses of steroids (eg, prednisone 5 to 7.5 mg daily) are permitted while on study, as is the use of local steroids.

Subjects who, in the assessment by the investigator, require the use of any of the aforementioned treatments for clinical management should be removed from treatment but continue in study for assessment of disease status and survival.

The exclusion criteria describe other medications that are prohibited in this study.

There are no prohibited therapies during the post-treatment follow-up period.

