5.4.7. Procedures for Subjects Exhibiting Serotonin Syndrome

As noted in [Section 1.3.2](#), there is a rare chance that epacadostat could cause an increase in serotonin levels in the brain that might trigger SS, when administered alone or in combination with other serotonergic agents. This syndrome has been most closely associated with use of MAOIs, meperidine, linezolid, or methylene blue; all of these agents are prohibited during the study ([Section 5.6.3](#)).

Selective serotonin reuptake inhibitors and SNRIs are permitted in the study. Serotonin syndrome usually manifests with autonomic changes, mental status changes, and neurological findings. These mild, moderate, and severe signs and symptoms of SS (summarized in [Table 11](#)) should be evaluated in the context of possible comorbid conditions as well.

The following procedures will be implemented if subjects exhibit the signs/symptoms of SS, including tremor; hyperreflexia; spontaneous, ocular, or inducible clonus; together with agitation, fever, diaphoresis, or muscle rigidity:

- Immediately interrupt all study treatment administration.
- Immediately interrupt any SSRI or SNRI administration.
- Provide appropriate medical management of the subject until all signs/symptoms are resolved (eg, IV fluids and/or sympathomimetic amines for hypotension, benzodiazepines for agitation, administration of 5-hydroxytryptamine antagonists such as cyproheptadine).
- If etiologies other than SS are excluded, INCB001158 and pembrolizumab administration may be resumed unless other AE management guidelines apply for the specific event.
- If subject chooses to remain in the study, restart treatment with epacadostat after the SSRI or SNRI has been discontinued, no sooner than 5 half-lives have elapsed for the specific SSRI or SNRI in question, and after resolution of signs/symptoms of SS. The SSRI or SNRI dosing MAY NOT be restarted.

- If subject chooses to withdraw from the study, or must restart treatment with SSRI or SNRI, the subject should be scheduled for a follow-up visit. Treatment with SSRI or SNRI may be initiated 2 weeks after resolution of signs and symptoms of SS.
- If a subject had experienced moderate or severe unconfounded SS in the opinion of the investigator, without concomitant SSRI or SNRI usage, or serotonergic concomitant medications, only INCB001158 and pembrolizumab administration may be resumed; epacadostat treatment should be permanently discontinued.

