6.2. Treatment

The treatment period begins on the day the subject receives the first dose of study treatment (Cycle 1 Day 1), as assigned in the IRT system, through the point at which the investigator determines the subject will be permanently discontinued from study treatment. Cycle 1 Day 1 must be no more than 21 days after the subject has signed the ICF. Dates for subsequent study visits will be determined based on this day and should occur within 3 days (\pm) of the scheduled date unless delayed for safety reasons. At Cycle 1 Day 1, results from screening visit evaluations should be reviewed to determine whether the subject continues to meet the eligibility requirements, as specified in the Protocol.

Subjects will have regularly scheduled study visits as outlined in [Table 14](#) and [Table 15](#), and toxicities will be monitored continuously and will be graded using the NCI CTCAE v4.03 criteria.

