6.3. End of Treatment

When the subject permanently discontinues all 3 study treatments, as outlined in Section [5.5](#), the EOT visit should be conducted. If the EOT visit coincides with a regular study visit, the EOT evaluations will supersede those of that scheduled visit, and the data should be entered in the EOT visit in the eCRF. The EOT visit may occur up to 5 days after receiving the final dose of study treatment. The subject should be encouraged to return for the safety follow-up visit.

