6.4. Follow-Up

6.4.1. Safety Follow-Up

The safety follow-up period is the interval between the EOT visit and the scheduled follow-up visits, which should occur 30 to 37 days (all subjects) and 90 to 97 days (Phase 1 and Phase 2 Part A only) after the final dose of study treatments. Adverse events and SAEs must be reported up until the date of the follow-up visits, or until toxicities resolve, return to baseline, or are deemed irreversible, whichever is longer. Reasonable efforts should be made to have the subject return for the follow-up visits and report any AEs that may occur during this period. If the subject cannot return to the site for the safety follow-up visit (eg, lives far away), the subject should be contacted by telephone for assessment of AEs and SAEs. Sites should document this contact in the source.

If a subject is scheduled to begin a new anticancer therapy before the end of the 90- to 97-day safety follow-up period, the safety follow-up visit should be performed before new anticancer therapy is started. Once new anticancer therapy has been initiated, the subject will move into the survival follow-up period.

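### Section 5.6.3 bars MAO-inhibiting drugs until 2 weeks after the last epacadostat dose, but its lead-in and last line lift every prohibition when treatment ends; the live-vaccine bullet has the same conflict

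*Combined protocol and SAP*

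**What the plan says.** Four statements in Section 5.6.3 bear on this:

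- The lead-in to the list: "Subjects are prohibited from receiving the following therapies during the screening and treatment periods of this study".
- The MAOI bullet, which also covers drugs with significant MAO inhibitory activity (Appendix C lists meperidine, linezolid and methylene blue). Use "is prohibited from 21 days before starting study treatment through 2 weeks after the final dose of epacadostat has been taken".
- The removal sentence. Subjects who, in the investigator's assessment, "require the use of any of the aforementioned treatments for clinical management should be removed from treatment but continue in study for assessment".
- The last line: "There are no prohibited therapies during the post-treatment follow-up period". It names no exception.

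The live-vaccine bullet in the same list also reaches past treatment. It bars live vaccines from 30 days before the first dose and for as long as the subject participates in the study.

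The periods are set in Section 6. Treatment runs "through the point at which the investigator determines the subject will be permanently discontinued from study treatment" (6.2). "The EOT visit may occur up to 5 days after receiving the final dose of study treatment" (6.3). "The safety follow-up period is the interval between the EOT visit and the scheduled follow-up visits" (6.4.1). Section 5.4.7 says of MAOIs, meperidine, linezolid and methylene blue that "all of these agents are prohibited during the study", and refers back to 5.6.3.

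**The concern.** The MAOI bullet sets a washout that continues after dosing has ended. The lead-in ends the whole list with the treatment period, and the last line states without qualification that nothing is prohibited afterwards. A site that relies on either of those general sentences can start an MAO-inhibiting drug on a day when the bullet still forbids it.

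Section 5.4.7 names these agents as the ones most closely associated with serotonin syndrome, and Section 8.9 makes the syndrome an Event of Clinical Interest. A patient with advanced cancer could plausibly need linezolid or meperidine soon after stopping treatment. The point survives Amendment 2: enrollment is halted, but Section 4.6.1 lets Phase 1 subjects stay on treatment, and each of them will eventually stop. What is at stake is a safety instruction. No efficacy or DLT analysis depends on it.

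**Working it through.** The plan gives no figure to reproduce, so the check compares the texts and then places them on a timeline.

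**Inputs**

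- Washout: 14 days after the last epacadostat dose (5.6.3, MAOI bullet).
- Start of follow-up: the EOT visit (6.4.1), 0 to 5 days after the final dose of study treatment (6.3).
- Later starts: the synopsis times EOT at up to 5 days after withdrawal from treatment, and withdrawal can come after a hold. Section 5.4.2 interrupts all three drugs for a DLT that is not life-threatening, and Table 9 withholds all three for many immune-related events. Under Section 5.4.10, a persistent event forces permanent discontinuation only after a delay of more than 4 weeks (more than 12 weeks for immune-related events).

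**Formula.** Let d be the number of days from the last epacadostat dose to the start of follow-up. Days on which the bullet prohibits and the last line permits = max(0, 14 − d).

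| Situation | d | Days in conflict |
|---|---|---|
| All drugs stop together, EOT the same day | 0 | 14 − 0 = 14 |
| All drugs stop together, EOT on day 5 | 5 | 14 − 5 = 9 |
| All drugs held 10 days, then discontinued with EOT that day (illustration) | 10 | 14 − 10 = 4 |
| Epacadostat stopped or held at least 14 days before follow-up | ≥ 14 | 0 |
| Discontinued after a delay of more than 4 weeks | > 28 | 0 |

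The range is therefore 0 to 14 days. For a simultaneous stop with a prompt EOT visit it is 9 to 14 days, that is 9/14 = 64% to 100% of the washout. The lead-in gives the same range when d is measured to the discontinuation decision, because that is where 6.2 ends the treatment period.

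**Does any text settle which rule wins?** None does.

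- The last line and the lead-in carry no exception, and the bullet does not say that it overrides them.
- The opening paragraph of 5.6.3 disallows drugs barred by the exclusion criteria while the study is ongoing. Section 5.4.7 bars these agents during the study. Both are at odds with the last line, but both are also broader than a two-week limit, so neither confirms the bullet's end date.
- The live-vaccine bullet meets the last line and the lead-in in the same way. Its ban lasts as long as participation, so it covers follow-up too.

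**The case against.** The strongest reply is that a specific, dated rule governs a general sentence. The bullet's two-week clause would do nothing unless it reached past treatment, and both lines sit in one short section, so a careful site would apply the bullet. That is very probably what the sponsor intends. It stands as an account of intent, but the protocol does not say so, and the last line is categorical.

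A second reply is that the wording is not the only protection. Questions on prohibited drugs go to the medical monitor (5.6.3), the sponsor or study monitor is notified at withdrawal (5.5.2), new AEs are monitored for at least 90 days in Phase 1 or until new anticancer therapy (8.1.2), and serotonin syndrome is reportable within 24 hours (8.9). This stands. A reader might infer that the wording is the main safeguard in the window, and the documents do not support that.

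Other stronger readings also fail:

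- A reader might take the removal sentence itself to contradict the bullet. It sets no start date for the drug. It only leaves the washout unmentioned, and it can be read together with the bullet.
- A reader might take 9 to 14 days as universal and multiply by 5 subjects to get 45 to 70 subject-days. The holds listed above can bring the overlap to zero, so there is no such lower bound. Even the upper figure would measure a wording overlap and not a risk.
- A reader might use the 2 of 958 subjects in Section 1.3.2 to predict events in this window. That rate is program-wide and not conditional on taking an MAO-inhibiting drug after the last dose, and the documents do not say how often such a drug would be needed.

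**Conclusion.** The inconsistency is real and confined to wording. The last line and the lead-in of 5.6.3 conflict with the MAOI bullet, and with the live-vaccine bullet in the same way. For MAO-inhibiting drugs the conflict lasts 0 to 14 days per subject. The 9-to-14-day part of that range assumes that all drugs stop together and that EOT falls within 5 days of the last dose.

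Its practical weight is small. Section 4.3.1 caps Phase 1 enrollment at 5 subjects. Section 1.3.2 reports that preclinical data make the syndrome unlikely even with linezolid, and that the reported episodes were mild and resolved. No estimate, population or decision rule changes. The correction is worth making because it concerns an operative safety rule, not because harm is expected.

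**What to change.** Reword the last line of 5.6.3 so that it opens with an exception: except where a bullet above states a longer period (MAOIs and the Appendix C drugs with significant MAO inhibitory activity, until 2 weeks after the final epacadostat dose; live vaccines, while the subject participates in the study), no therapy is prohibited in post-treatment follow-up. Add to the lead-in: unless a longer period is stated below. An exception for MAOIs alone would leave the live-vaccine conflict in place.

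Urgent care is not blocked, because the opening paragraph of 5.6.3 leaves the final decision on supportive therapy with the investigator and/or the primary physician. No new data are needed, since Section 5.6 already records concomitant medications for 30 days after the last dose, or until new anticancer therapy if sooner. The cost is one clause, one phrase, and the sponsor and IRB/IEC approval that Section 10.1 requires for protocol changes. It can be bundled with any other amendment.
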